5.2 Objective Response Rate

Objective response rate is a secondary objective for this study. With a sample size of 114 subjects, there will be at least 90% power to detect a 23% improvement in response rate, using a two-sided 0.2 level test, in the E-Pd arm (to 58%) compared with a response rate of 35% in the Pd arm.

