4.1.2 Objective Response Rate (ORR)

The best overall response is determined as the best assessment based on all on-study efficacy data for the subject.

Objective response rate is defined as the proportion of randomized subjects who achieve a best response of stringent complete response (sCR), complete response (CR), very good partial response (VGPR) or partial response (PR) using the modified IMWG criteria as per investigator's assessment.

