5.1 Progression-Free Survival

The primary objective of the study is to compare the progression-free survival between the treatment arms in all randomized subjects. The number of events and power of this study were calculated assuming an exponential distribution for PFS in each arm.

The study will require at least 71 PFS events (progressions or deaths), for a two-sided experiment-wise $\alpha = 0.2$ log-rank test, to show a statistically significant difference in PFS between the treatment arms with 85% power when the true hazard ratio of the experimental arm to the control arm is 0.57. This is equivalent to demonstrating an improvement in median PFS from 4.0 months in the Pd arm⁹ to a median PFS of 6.8 months in the E-Pd arm.¹ A total of 105 subjects are to be randomized. Assuming approximately 10% of subjects may be lost to follow-up for the primary endpoint data, an additional 9 subjects would be randomized in the study. It is estimated that it would take approximately 9 months for full accrual of 114 subjects (assuming a fixed accrual rate of 13 subjects per month) and another 6 months to obtain the required number of events.

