7.5.2 Analysis of Objective Response

The number and percentage of subjects in each category of best overall response per investigator assessment (stringent complete response [sCR], complete response [CR], very good partial response [VGPR], partial response [PR], minor response [MR], stable disease [SD], progressive disease [PD], or unable to determine [UD]) will be presented by treatment group. An estimate of the response rate and an associated exact two-sided 95% CI (Clopper and Pearson¹³) will be computed, by treatment group.

One of the secondary objectives is to compare the ORR in the two treatment groups using a two-sided $\alpha = 0.2$ level Cochran-Mantel-Haenszel (CMH) test stratified by the same factors used in the analysis of PFS. An estimate of the treatment odds ratio and corresponding two-sided 80% CI will be computed. A two-sided 95% CI will also be computed.

A 2-sided, 80% CI (along with 95% CI) for the difference of ORR between treatment arms will be computed for all randomized subjects by the method of DerSimonian and Laird¹⁴, using a fixed-effects model (setting Δ^2 equal to zero), adjusting for the stratification factors. The weighted response rate difference and 80% CI (along with 95% CI) can be determined using the following formula:

$$\hat{\theta} = \frac{\sum_{i=1}^4 \hat{\theta}_i w_i}{\sum_{i=1}^4 w_i} \sim N(\theta, 1 / \sum_{i=1}^4 w_i)$$

where $\hat{\theta}_i$ is the response rate difference of the i^{th} stratum and $w_i = 1/\text{var}(\hat{\theta}_i)$.

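### SAP 5.2 gives the ORR comparison at least 90% power, but its own inputs give just under 90% (about 89%), assuming 1:1 allocation

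*SAP*

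**What the plan says.** SAP 5.2 states "With a sample size of 114 subjects, there will be at least 90% power to detect a 23% improvement in response rate". The rates behind this claim are 35% for Pd and 58% for E-Pd, and the level is 0.2, two-sided. SAP 7.5.2 names the test as a "Cochran-Mantel-Haenszel (CMH) test stratified by the same factors used in the analysis of PFS", also at two-sided 0.2. Those factors are the number of prior lines (2-3 vs. ≥ 4) and ISS stage (I-II vs. III), which makes four strata.

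SAP 4.1.2 sets the denominator: "Objective response rate is defined as the proportion of randomized subjects who achieve a best response of stringent complete response". Any response of PR or better counts. Best response there draws on all on-study efficacy data. Protocol 8.3.2.1 also uses randomized subjects.

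SAP 5.1 starts from 105 subjects and adds 9, with the reason "Assuming approximately 10% of subjects may be lost to follow-up for the primary endpoint data". The primary endpoint is PFS. SAP 5.2 makes no separate allowance for subjects without a response assessment.

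**The concern.** The SAP words the ORR power as a lower bound, yet the inputs it gives do not reach that bound by the usual two-sided calculations. About 90% would pass as rounding; at least 90% claims a margin that is not there.

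The basis of the two response rates is also unstated. In an analysis of all randomized subjects, someone who leaves before a confirmed response counts as a non-responder. Whether the assumed rates already reflect that affects how far the stated power can be relied on.

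Little is at stake. ORR is a secondary endpoint of a phase 2 trial, but it has its own formal test. The type II error is about 10% to 12%, where the SAP implies no more than 10%.

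**Working it through.** **Inputs.** From SAP 5.2: p1 = 0.35 (Pd), p2 = 0.58 (E-Pd), N = 114, two-sided α = 0.2, so z = 1.2816. Stated power: at least 90%.

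**Allocation (assumption).** The ratio is not in the visible text; I take 1:1, so n = 57 per arm. This fits the PFS design. For HR 0.57, two-sided 0.2 and 85% power, the Schoenfeld formula at 1:1 gives 4 × (1.2816 + 1.0364)² / (ln 0.57)² = 4 × 5.373 / 0.3160 = 68.0, rounded up to 69 events, against 71 stated. At 2:1 it gives 5.373 / (2/9 × 0.3160) = 76.5.

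**Stated figure, pooled z.** The mean rate is 0.465.
- Null SE = √(2 × 0.465 × 0.535 / 57) = 0.09343
- Alternative SE = √((0.35 × 0.65 + 0.58 × 0.42) / 57) = √(0.4711 / 57) = 0.09091
- (0.23 − 1.2816 × 0.09343) / 0.09091 = 1.213, so power is **88.7%**

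**Unpooled z.** 0.23 / 0.09091 − 1.2816 = 1.248, so power is **89.4%**.

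**Other methods, 57 per arm.**

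| Method | Power |
|---|---|
| Arcsine | 88.5% |
| Exact power of the Pearson chi-square, unstratified | 89.8% |
| Stratified CMH, four strata, simulated | about 88% to 89% |
| Fisher exact test | 86.0% |
| Continuity-corrected z | 84.6% |

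The exact chi-square figure is slightly flattering: at a common rate of 46.5% that test rejects about 22% of the time, not 20%. The CMH figure depends on assumed strata shares and on how evenly the arms fall within strata. A check with the same rates in every stratum and perfect balance within strata came closer to 90% but stayed below it. Fisher and the continuity correction are conservative and are not the planned test.

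**Other readings.** A one-sided 0.2 test would give 95.2%, but the SAP says two-sided. Allocation of 2:1 would give 85.8%.

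**Sample size for 90%.** The pooled formula needs 61 per arm. This is not a firm threshold, because exact chi-square power moves up and down with n: 90.4% at 58 per arm and 89.5% at 61.

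**Sensitivity only.** Suppose 35% and 58% are rates among evaluable subjects and a fraction d of each arm is lost before a confirmed response. The rates among all randomized subjects are then multiplied by (1 − d), with n still 57.

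| d | Rates | Pooled | Unpooled | Exact chi-square |
|---|---|---|---|---|
| 0 | 35.0% vs 58.0% | 88.7% | 89.4% | 89.8% |
| 5% | 33.25% vs 55.1% | 86.3% | 87.0% | 87.5% |
| 10% | 31.5% vs 52.2% | 83.7% | 84.4% | 84.8% |

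The documents give no value of d for ORR; 10% is borrowed from the PFS allowance.

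**The case against.** The strongest objection is that the gap is rounding. The rates are whole percentages: 58.3% in place of 58% would lift exact chi-square power to 90.4%, and the main approximations already lie within 2 points of 90%. No decision rule in the visible text depends on this figure, and an ORR result would be read from its estimate and the planned 80% and 95% intervals. Most of this stands and keeps the point minor. It does not rescue a stated floor, because at exactly 35% and 58% none of the two-sided 1:1 calculations above reaches 90%.

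A reader might infer two stronger points that the documents do not support.

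- **That using all 114 is an error.** It is the right denominator, since SAP 4.1.2 defines ORR on randomized subjects.
- **That the true power is about 84%, because SAP 5.1 expects 10% loss.** That 10% is for the primary endpoint, PFS. A subject who has a confirmed response and is lost later still counts as a responder. If the 35% and 58% are already rates among all randomized subjects, multiplying by 0.9 counts the loss twice.

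The 84% does have some basis as a bad case. Protocol 5.4.2 and 5.4.4 require PR or better on two consecutive assessments, before any new therapy, so very early leavers cannot become responders. It still needs every lost subject in both arms to leave that early.

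**Conclusion.** The point holds as a small overstatement. With 57 per arm, 35% vs 58% and a two-sided 0.2 level, power is about 89%: 88.7% to 89.8% by the z and exact chi-square calculations, and about 88% to 89% for the planned CMH test. The stated floor is missed by roughly 0.2 to 2 points. This rests on 1:1 allocation, which is assumed here, and for CMH on assumed strata.

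The SAP also leaves open which population the two rates describe. Power of about 84% (about 86% to 87% at 5% loss) belongs only in a labelled worst-case sensitivity statement. Nothing here supports a larger trial. Severity: minor.

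**What to change.** In SAP 5.2, replace the claim of at least 90% power with about 89% power, keeping the 114 subjects, the 35% and 58% rates and the two-sided 0.2 level. Add a sentence saying whether those rates are proportions of all randomized subjects.

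If they are rates among evaluable subjects, a sensitivity sentence may follow: should 10% of each arm be lost before a confirmed response and count as non-responders, power would be about 84%. Label this as a worst case and say that the 10% is borrowed from the PFS allowance.

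Do not change the sample size, the test or the analysis population. The cost is one or two sentences and a slightly less favourable figure.

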5.3 Overall Survival

OS is another secondary objective for this study. The final analysis of OS will be conducted after at least 78 deaths have been observed from 114 subjects. This is expected to happen 18 months (1.5 years) from the time of the final PFS analysis. With 78 events the study will have 75 % power using a two-sided log-rank test at a $\alpha = 0.2$ level, to show a statistically significant difference when the true hazard ratio is 0.64. This is equivalent to demonstrating a 56% improvement in median OS, i.e., 19.8 months in the E-Pd arm compared to the median OS in the Pd arm of 12.7 months.⁹

6 STUDY PERIODS, TREATMENT REGIMENS AND POPULATIONS FOR ANALYSES

6.1 Study Periods

There are three periods in this study: screening, on-treatment and post-treatment follow-up.

Screening: Most screening procedures must be done no more than 14 days prior to randomization. Some exceptions include efficacy assessments and ECGs, which can be done up to 28 days prior to randomization, and bone marrow which can be done up to 35 days prior to randomization. See Section 5 of the Protocol for full details of study procedures and timings. For analyses purposes

¹ Meletios A. Dimopoulos, Martha Q Lacy, et al. Pomalidomide in Combination with Low-Dose Dexamethasone: Demonstrates a Significant Progression Free Survival and Overall Survival Advantage, in Relapsed/Refractory MM: A Phase 3, Multicenter, Randomized, Open-Label Study Blood (ASH Annual Meeting Abstracts), Nov 2012; 120: LBA-6.

All enrolled subjects: All subjects who gave signed informed consent and who were entered in the IVRS.

Randomized subjects: All enrolled subjects who were randomized.

Treated subjects: This population includes all randomized subjects who received at least one dose of study medication (pomalidomide, dexamethasone or elotuzumab).

PK evaluable subjects: All treated subjects with at least one elotuzumab serum concentration data.

The analysis of baseline characteristics, efficacy and subject-reported outcomes will be carried out on the Randomized subjects population, with subjects grouped according to the treatment arm to which they were randomized. The analysis of extent of exposure and safety will be based on the Treated subjects population, with subjects grouped according to the treatment received, where treatment received is defined as the treatment arm to which they were randomized, unless they received the wrong treatment throughout the study.

[REDACTED]

[REDACTED]

[REDACTED]

[REDACTED]

[REDACTED]

[REDACTED]

[REDACTED]

7.2 Study Conduct

7.2.1 Accrual Patterns

Tables summarizing accrual by center, country, region (North America, Europe, Japan, and Australia) overall and by treatment group will be generated (see [Appendix 3](#) for a list of countries in each region). Subject accrual will also be summarized by the randomization stratification factors per IVRS (number of lines of prior therapy (2-3 vs. ≥ 4) and ISS Staging at study entry (I-II vs. III)), overall and by treatment group. In addition, this summary will also be presented based on the stratification information obtained from the baseline CRF pages. A cross tabulation of IVRS vs. Baseline stratification factors will also be summarized.

7.2.2 Protocol Violations

A relevant protocol deviation is defined as a deviation from the protocol which is programmed in the database and which could potentially affect the interpretability of the study results.

The number and percentage of subjects with any relevant protocol deviation and each specific deviation will be presented overall and by treatment group.

The following eligibility deviations are considered relevant in this study and will be summarized for all treated subjects:

- 1) Number of prior systemic anti-myeloma therapy is < 2
- 2) Non-measurable disease. This occurs when none of the following three conditions are met:
 - Serum IgG, IgA, or IgM M-protein $\geq 0.5\text{g/dL}$
 - M-protein $\geq 200\text{mg}$ in 24-hour urine
 - Involved serum free light chain (sFLC) $\geq 100\text{ mg/dL}$ provided the FLC ratio is abnormal
- 3) Ineligible for this study due to failure to meet criteria for refractory or relapsed and refractory MM. This occurs when:
 - Subjects did not progress (on or within 60 days of treatment) to their last treatment (not refractory).
 - Subjects did not fail treatment with a proteasome inhibitor and lenalidomide. This occurs when none of these take place:
 - i) “Refractory” to proteasome inhibitor and lenalidomide, and to their last treatment.
 - ii) “Relapsed and refractory” = patients had achieved at least a partial response to previous treatment with proteasome inhibitor or lenalidomide, or both, but progressed within 6 months, and were refractory to their last treatment.

Also, the following on-treatment deviations are considered relevant in this study and will be summarized for all treated subjects:

- 4) Non-protocol specified systemic anti-myeloma therapy prior to discontinuation of study therapy
- 5) Received non-assigned treatment regimen throughout the study
- 6) No baseline efficacy assessment. This occurs when there are no tumor assessments at all (laboratory assessments) on or prior to first day of dosing.
- 7) Subjects continuing to receive study therapy after 10 weeks of documented progression per investigator (as progression needs to be confirmed).

If assessments based on the central laboratory is unavailable, but the local laboratory results are available, then those will be used for evaluating deviations 2 and 6.

A by subject listing of relevant protocol deviations will be provided.

[REDACTED]

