3.3.1 Inclusion Criteria

1) Signed Written Informed Consent

- a) Subject is, in the investigator's opinion, willing and able to comply with the protocol requirements.
- b) Subject has given voluntary written informed consent before performance of any study-related procedure not part of normal medical care, with the understanding that consent may be withdrawn by the subject at any time without prejudice to their future medical care.

2) Target Population

- a) Must have received ≥ 2 prior lines of therapy (See Appendix 1) which must have included at least 2 consecutive cycles of lenalidomide and a proteasome inhibitor alone or in combination.
- b) Documented refractory or relapsed and refractory (R/R) multiple myeloma
- c) Refractory (progressed on or within 60 days of treatment) to their last treatment.
- d) Subjects must have failed treatment with a proteasome inhibitor and lenalidomide in one of the following ways⁴¹.
 - i) "Refractory" to proteasome inhibitor and lenalidomide, and to their last treatment.
 - ii) "Relapsed and refractory"= patients had achieved at least a partial response to previous treatment with proteasome inhibitor or lenalidomide, or both, but progressed within 6 months, and were refractory to their last treatment.

- e) Measurable disease at screening, based on central lab results, defined as one or more of the following:
 - i) Serum IgG, IgA, or IgM M-protein ≥ 0.5 g/dL (5 g/L).
 - ii) Urine M-Protein ≥ 200 mg (0.2 g) excreted in a 24-hour collection sample
 - iii) Involved serum free light chain (sFLC) ≥ 100 mg/L (10 mg/dL) provided the FLC ratio is abnormal.
- f) Eastern Cooperative Oncology Group (ECOG) performance status ≤ 2 .

3) Age and Reproductive Status

- a) Males and Females at least 18 years or legal age of consent per local regulations.
- b) Women of childbearing potential (WOCBP) must have two negative serum or urine pregnancy tests (minimum sensitivity 25 mIU/mL or equivalent units of HCG). One 10-14 days prior to start of the study drug and one 24 hours prior to the start of study drug. See [Section 3.3.3](#) for the definition of WOCBP.
- c) Women must not be breastfeeding.
- d) WOCBP must agree to follow instructions for method(s) of contraception for 4 weeks before the start of treatment with study drugs, for the duration of treatment with study drugs, and for a total of 120 days post-treatment completion.

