5.4.1 Primary Efficacy Assessment

Response criteria in [Appendix 6](#)^{32,33} will be used for the efficacy analysis. For the purposes of this study, all subjects' tumor assessments by myeloma laboratory tests (SPEP M protein and UPEP M protein quantification, corrected calcium (calcium and albumin), and serum free light chain) should be re-evaluated per the protocol-stated frequency relative to the date of first dose of study drug until disease progression based on [Appendix 6](#), irrespective of dose delays or treatment cycle. **If subject does not have documented disease progression as defined in [Appendix 6](#) at the time of study drug discontinuation, then tumor assessments must continue to be performed according to the same schedule described above until disease progression even if a subsequent anti-myeloma treatment is initiated prior to disease progression.** Subjects will be followed every 12 weeks, or more frequently, after disease progression for survival, subsequent myeloma therapy, and development of second primary malignancy.

All efficacy laboratory assessments (SPEP, UPEP, serum/urine immunofixation, and sFLC) should be done through the central laboratory, except corrected calcium (serum calcium and serum albumin), and bone marrow assessments for plasma cell percentage and light chain restriction (clonality by IHC or flow cytometry). All bone marrow aspirate and core biopsy samples should be assessed locally. For any SPEP, UPEP, or sFLC assessment performed locally, in lieu of a central lab assessment, (ie, if the subject cannot complete a visit at the study site), M protein absolute quantification (eg, g/dL or g/L) or sFLC (eg, mg/L or mg/dL) must be performed. Any laboratory samples analyzed locally, including for efficacy, must be entered on the appropriate CRF/eCRF as requested by the Sponsor to properly assess efficacy per protocol criteria.

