5.4.2 Laboratory Assessments for Myeloma

All laboratory efficacy assessments must be performed until disease progression or withdrawal of consent, even if the subject is discontinued from study therapy and has started new myeloma therapy. Confirmation of \geq PR is required on 2 consecutive assessments for Serum, Urine and sFLC.

- 1) **Serum:** SPEP for M protein quantification, total serum protein, serum immunofixation, and quantitative immunoglobulin assay.
 - a. Serum Immunofixation is required at baseline and to confirm CR regardless of whether measurable M-protein was present at baseline.
 - b. Subjects with measurable disease in SPEP will be assessed for response based on SPEP and not by the serum FLC assay.
 - c. Subjects with measurable disease in both SPEP and UPEP will be assessed for response based on these two tests and not by the serum FLC assay.
 - d. All other serum tests will be followed at each tumor assessment.
- 2) **Serum free light chain (sFLC):**
 - a. Subjects without measurable serum M-protein (ie, < 0.5 g/dL (5 g/L)) or urine M-protein (ie, < 200 mg (0.2 g) per 24 hours) and considered oligosecretory must have sFLC assessed at each cycle until until progression.
 - b. Serum must be collected at screening and time of serum and urine IFE negativity to confirm CR and be sent to the central lab for sFLC analysis. This measurement is required to assess for sCR
- 3) **Urine:** 24-hour urine collection for M protein quantification, urinary light chains, and immunofixation. 24-hour urine must be collected with each cycle for all subjects.
 - a. Urine Immunofixation is required at baseline and to confirm CR, regardless of whether measurable M-protein was present at baseline.
 - b. All other urine tests will be followed at each tumor assessment.
- 4) **Bone marrow aspiration/biopsy:**

Table 5.4.2-1: Bone Marrow Samples		
Sample	Local Laboratory	Central Laboratory

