7.3.3 Disease Characteristics at Baseline

Baseline disease characteristics will be summarized, overall and by treatment group. The following parameters will be presented to summarize baseline disease:

- Serum M-protein (g/L)

- Urine M-protein (g/24 hours)
- Serum free light chain (g/L)
- Myeloma type (IgG, IgA, IgM, Light chain disease)
- Number of lytic bone lesions (0, 1-3, >3)
- Myeloma risk category
 - High risk: ISS stage II or III **and** t(4;14) or del(17p) abnormality
 - Low risk: ISS stage I or II **and** absence of t(4;14), del(17p) and 1q21 abnormalities and age < 55 years
 - Standard risk: any subjects not meeting the definition of high or low risk.
 - Not Evaluable: Subjects with missing data preventing their classification in the other 3 categories
- Individual FISH abnormalities (del 17p, t(14; 16), t(4; 14), del(1q), and del(1p))
- $\beta 2$ microglobulin (mg/L) (<3.5, ≥ 3.5 -5.5, ≥ 5.5)
- Albumin (g/L) (<3.5, ≥ 3.5)
- LDH (<300 IU/L, ≥ 300 IU/L)
- Soft tissue plasmacytomas (Yes, No)
- Refractory Status to prior lines of therapy:
 - Refractory to lenalidomide
 - Relapsed and refractory to lenalidomide
 - Refractory to proteasome inhibitor (PI)
 - Relapsed and refractory to proteasome inhibitor (PI)
 - Refractory to both PI and lenalidomide
 - Relapsed and refractory to both PI and lenalidomide
- ISS Stage (I, II, III) at enrollment and at diagnosis
- Time from disease diagnosis to randomization (months)

An accompanying by-subject listing of disease characteristics at baseline will be presented. All reports will be presented in standard international (SI) units and summaries in US units will also be available.

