7.5.1.1 Supportive Analyses of Progression-Free Survival

The following supportive analyses will be conducted using both the ITT and the secondary definitions of PFS. P-values provided for these analyses are descriptive and will be used to evaluate the results in context of the primary analyses.

- 1) A multivariate Cox regression model will be used in order to estimate the treatment effect after adjustment for possible imbalances in known or potential prognostic factors. The factors used in the randomization, which, by definition, will be balanced across arms, will still be included in the model as stratification factors. However, all additional factors will be incorporated as covariates. The additional factors, which are all measured at baseline, will include: age (< 75 vs. ≥ 75), gender (male vs. female), ECOG PS (0-1 vs. 2), prior stem cell transplantation (yes vs. no), high myeloma risk (yes vs. no) [see [Section 7.5.1.2](#) for details], time from initial diagnosis, creatinine clearance (<60ml/min vs. ≥ 60 ml/min), and LDH (< 300IU/L, ≥ 300 IU/L).

The level of the covariate normally associated with the worst prognosis will be coded as the reference level:

- Age: ≥ 75
- Gender: Female
- ECOG: 2
- Prior stem cell transplantation: Yes
- High myeloma risk: Yes
- Time from initial diagnosis (\geq median)
- Creatinine clearance: < 60 ml/min
- LDH (≥ 300 IU/L)

The p-value associated with treatment and with each of the baseline covariates will be presented. The hazard ratio along with the associated 95% CI will also be presented. In addition, an 80% CI will be provided for the treatment effect.

- 2) PFS using stratification factors as obtained from the baseline CRF pages (instead of IVRS). The p-value and the hazard ratio associated with treatment will be presented along with the associated 2-sided 80% and 95% CIs. This analysis will be performed only if there is a difference of 10% in strata between the IVRS and CRF pages.
- 3) PFS using an un-stratified log rank test. The p-value and hazard ratio associated with treatment will be presented along with its associated two-sided 80% and 95% CIs.
- 4) PFS using an unstratified Cox proportional hazards model, adjusted, using as covariates only the two stratification factors used in randomization. The p-value and hazard ratio associated with treatment will be presented along with its associated two-sided 80% and 95% CIs.

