- 5) PFS for subjects with no relevant deviation. These analyses will be conducted only if there are more than 5% subjects with relevant protocol deviations. The p-value and hazard ratio associated with treatment will be presented along with its associated two-sided 80% and 95% CIs.

A by-subject listing will be presented including treatment arm, PFS duration under the primary definition, PFS duration under the secondary definition, whether the subject was censored under the primary definition, and if censored, the reason, and whether the subject was censored under the secondary definition, and if censored, the reason.

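### SAP 7.2.2 sets the sFLC limit for measurable disease ten times higher than the protocol, so eligible sFLC-only subjects may be reported as relevant deviations

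*SAP*

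**What the plan says.** Protocol 3.3.1, item 2(e), accepts any one of three findings as measurable disease at screening, judged on central laboratory results: serum M-protein of at least 0.5 g/dL, urine M-protein of at least 200 mg in 24 hours, or "Involved serum free light chain (sFLC) ≥ 100 mg/L (10 mg/dL) provided the FLC ratio is abnormal".

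SAP 7.2.2, item 2, turns this into a relevant eligibility deviation that applies when none of the three is met. The serum and urine limits are the protocol's. The third is "Involved serum free light chain (sFLC) $\geq 100\text{ mg/dL}$ provided the FLC ratio is abnormal". If central results are missing but local ones exist, "those will be used for evaluating deviations 2 and 6".

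Item 5 of SAP 7.5.1.1 uses the flag again, as follows: "PFS for subjects with no relevant deviation. These analyses will be conducted only if there are more than 5% subjects with relevant protocol deviations". Near its start, that section also says: "The following supportive analyses will be conducted using both the ITT and the secondary definitions of PFS". SAP 7.5.3 repeats the supportive analyses for OS, and SAP 8.7 lists relevant eligibility deviations among the topline outputs.

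**The concern.** The SAP item exists to detect departures from the protocol's own eligibility rule, so its limit should be the protocol's limit. Here the number 100 was kept but the unit changed from mg/L to mg/dL. Neither document gives a reason.

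The subjects exposed are those followed by sFLC alone, and the plan expects such subjects. Protocol 5.4.2 says that those without measurable serum or urine M-protein "and considered oligosecretory must have sFLC assessed at each cycle".

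The unit needs to be explicit because sFLC appears in more than one. Local results may come in either of two units under Protocol 5.4.1 ("or sFLC (eg, mg/L or mg/dL) must be performed"), and the SAP 7.3.3 baseline summary uses a third ("Serum free light chain (g/L)").

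At stake are a misstated deviation rate and a supportive analysis that could drop eligible subjects while claiming to drop ineligible ones.

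**Working it through.** **1. Units (1 dL = 0.1 L).**
- Protocol: 100 mg/L × 0.1 = 10 mg/dL, which reproduces the protocol's own pair of figures. This is 0.1 g/L.
- SAP: 100 mg/dL ÷ 0.1 = 1000 mg/L, or 1.0 g/L.
- Ratio: 1000 / 100 = 10.

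**2. Both rules applied to a subject with no measurable serum or urine M-protein and an abnormal FLC ratio.**

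| Involved sFLC (mg/L) | Measurable under protocol | Measurable under SAP |
|---|---|---|
| 99 | no | no |
| 100 | yes | no |
| 500 | yes | no |
| 999 | yes | no |
| 1000 | yes | yes |

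The rules disagree from 100 to below 1000 mg/L (10 to below 100 mg/dL) and nowhere else. A subject with measurable serum or urine M-protein is not affected, because the deviation needs all three conditions to fail.

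**3. The 5% trigger.** The analysis is run when k/N > 0.05. The smallest such k is:
- N = 99: 5 (5/99 = 5.05%)
- N = 100: 6 (5/100 is exactly 5%, which is not more than 5%)
- N = 105: 6 (6/105 = 5.7%)
- N = 114: 6 (6/114 = 5.3%)
- N = 119: 6 (6/119 = 5.04%)
- N = 120: 7 (6/120 is exactly 5%)

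SAP 7.5.1.1 does not name the denominator. SAP 7.2.2 summarises deviations in treated subjects, which is the natural candidate. With 114 subjects planned (105 before the allowance for loss, SAP 5.1), the answer is 6 on any denominator from 100 to 119. False flags therefore change whether the analysis is run only if true relevant deviations number 5 or fewer and the false ones bring the total to at least 6.

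**4. Precision lost if the analysis is run.** The documents do not give the number wrongly excluded, m, so 1, 3 and 6 are illustrative. If events fall in proportion to subjects, the standard error of the log hazard ratio grows by sqrt(114/(114 − m)) − 1:
- m = 1: sqrt(114/113) − 1 = 0.44%
- m = 3: sqrt(114/111) − 1 = 1.34%
- m = 6: sqrt(114/108) − 1 = 2.74%, with 71 × 108/114 = 67.3 expected events instead of 71

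**The case against.** The mismatch itself is not in dispute; the case against concerns how much it matters.

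- **The harm is small.** The band may be empty. The flag rests on a baseline value, so it does not by itself favour an arm. The only analysis touched is conditional and supportive, with p-values that SAP 7.5.1.1 calls descriptive. All of this stands and limits the consequence. It does not make the limit right.
- **SAP 7.2.2 opens by defining a relevant deviation as a departure from the protocol.** A subject at 10 to below 100 mg/dL has not departed from it, so a careful programmer might use the protocol's figure. But the same sentence says these deviations are programmed in the database, and item 2 is the specification for that program. The definition lowers the risk without removing it.
- **The mixed units prove little.** Eligibility is based on central results, so local values should be the exception, and g/L is only a reporting unit. That is fair: the mixed units are a reason to state the unit clearly, not evidence of the error.
- **It may be too strong to call the primary analysis safe.** SAP 4.1.1.1 makes an adequate assessment depend on whether sFLC was measurable at baseline, and SAP 4.1.1.3 censors primary PFS at the last adequate assessment. SAP 4.1.1.1 gives no number and does not refer to 7.2.2, so no effect is shown. The safe statement is that the deviation flag does not enter the primary test. Whether the 7.2.2 limit was reused in the adequacy rule is worth checking.

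The by-subject sFLC listing in SAP 7.5.5 could expose the error, but only if someone compares it with the protocol.

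**Conclusion.** The SAP is wrong as written: its sFLC limit is ten times the criterion it is meant to check, and no other passage corrects it. The mismatch is certain. How many subjects it affects is unknown.

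Harm requires that the deviation is coded from the SAP text and that at least one sFLC-only subject falls in the band. The deviation table, the by-subject listing and the topline output would then overstate ineligibility. If the 5% trigger is also met, eligible subjects would be dropped from the no-deviation analyses of PFS (both definitions) and OS, with a modest loss of precision on the illustrative counts above. The comparisons of PFS, ORR and OS in all randomized subjects do not use the flag. This should be fixed, but it does not threaten the trial's main conclusion.

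**What to change.** In SAP 7.2.2, item 2, replace 100 mg/dL with 100 mg/L (10 mg/dL), so that all three limits match Protocol 3.3.1, item 2(e). In the dataset specification, convert central and local sFLC results to one stated unit and apply 100 mg/L (0.1 g/L) before deviations are derived. At the same time, confirm that any rule for sFLC measurable at baseline under SAP 4.1.1.1 uses the same figure.

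The cost is one unit in the SAP, one line in the specification and a short programming check. Design, sample size and the primary analysis stay as they are.
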